Safety Profile: Systemic and hematologic: Pioglitazone may be associated with hypoglycemia, edema, anemia (lower hemoglobin levels and hematocrit due to edema), weight gain (increased fat cell differentiation), and/or ovulation in premenopausal, anovulatory women. The most common adverse events (≥5%) reported to date include upper respiratory tract infection, headache, sinusitis, myalgia, tooth disorder, aggravated diabetes mellitus, and pharyngitis.

Gastrointestinal (GI)/Liver: Reports of hepatitis and of hepatic enzyme elevations to three or more times the upper limit of normal (ULN) have been reported with pioglitazone. Very rarely, these reports have involved hepatic failure with or without fatal outcome, although causality has not been established. Liver enzymes, including serum ALT, need to be evaluated in all patients at initiation of therapy with pioglitazone, and periodically thereafter. If ALT >2.5X ULN at baseline or if the patient exhibits clinical evidence of active liver disease, pioglitazone will be discontinued.

Systemic: Like other thiazolidinediones (TZDs), pioglitazone can cause fluid retention when used alone or in combination with other anti-diabetic agents, including insulin. Fluid retention may lead to or exacerbate heart failure. However, in the context of pancreatic cancer, these potential issues seem relatively minor. Nevertheless, we will exclude patients with a history of previously existing cardiac disease.

Cardiovascular: The Endocrinologic and Metabolic Drugs and Drug Safety and Risk Management Advisory Committees to the FDA recently met jointly to review the cardiovascular ischemic/thrombotic risks of the thiazolidinediones (TZDs) class, with focus on rosiglitazone. At this stage, there were no concerns raised with respect to the cardiovascular safety of pioglitazone.

Pioglitazone has been prescribed in many patients with pancreas cancer who have a diagnosis of type 2 diabetes mellitus in routine clinical practice. To our knowledge, no unexpected serious adverse events have been reported in patients with pancreas cancer receiving treatment with pioglitazone.

Table 1: Adverse Effects of Pioglitazone

Placebo-Controlled Clinical Studies of ACTOS Monotherapy: Adverse Events Reported at a Frequency ≥ 5% of Patients Treated with ACTOS

(% of Patients)		
Adverse Effects	Placebo N=259	ACTOS N=606
Upper Respiratory Tract Infection	8.5	13.2
Headache	6.9	9.1
Sinusitis	4.6	6.3
Myalgia	2.7	5.4
Tooth Disorder	2.3	5.3

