We plan to enroll fifteen patients with metastatic or locally advanced pancreas cancer into a double arm pilot exploratory study of oral pioglitazone 45 mg daily.

Treatment will be administered for 8 weeks and then stopped.

Control Arm:

Up to ten patients meeting eligibility criteria will be enrolled in the control arm. Patients will be treated per standard of care treatment at the discretion of the treating team and will not be treated with pioglitazone.

Treatment arm assignment:

Treatment arm will be assigned by the principal investigator or treating MD at their discretion. Given the exploratory nature of this study, randomization will not be performed.

Control arm patients can include the following examples:

- patient declines pioglitazone therapy but agrees to biomarker testing (Adiponectin, a hormone made by fat cells, will be measured). Additional assays may be performed
- Patient is enrolled in another clinical trial which does not allow experimental therapy (pioglitazone) to be given. The protocol of the patient's study will be reviewed to ensure biomarker testing (Adiponectin, a hormone made by fat cells, will be measured) as defined in this study is not specifically prohibited.

- Patients enrolled after completion of the 15 study arm patients
- Other patients as deemed appropriate by the PI or co-Is

A. Recruitment

Eligible study patients will be screened, recruited, and enrolled at the following institutions:

1. University of Texas Southwestern Medical Center at Dallas:
 - a. Harold C. Simmons Comprehensive Cancer Center
 - b. University Hospital – Zale Lipshy
 - c. University Hospital – Saint Paul
2. Parkland Health and Hospital System (PHHS)
3. VA North Texas (Dallas)

Study patients will be recruited from the practices of the PI and co- investigators. Potentially eligible patients will be approached by their health care providers who can refer them to the study coordinator for screening. All patients being considered for the study and eligible must sign an informed consent for the study prior to any study specific procedures.

IX. Eligibility Criteria

Inclusion Criteria

Inclusion Criteria	Reason
Signed informed consent	Document patient participation and understanding of study requirements
Histologically proven adenocarcinoma of the pancreas	Disease of interest
Radiologically measurable disease	Target lesion to follow response to therapy

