ECOG functional status 0-2	Those with worse functional status may not have reasonable survival to demonstrate meaningful follow up

Exclusion Criteria	Reason
Prior radiation therapy for pancreatic cancer	Radiation effect can alter metabolic effects of the pancreas. If patient has measurable disease which has not been radiated, they may be enrolled.
If chemotherapy is planned, new chemotherapy regimen should have started no more than 21 days prior to enrollment	Start pioglitazone as close to the start of a chemotherapy regimen
Surgery or radiation planned within 8 weeks of starting therapy	Allow adequate exposure to TZD (minimum 8 weeks)

Prior exposure to Thiazolidinedione (TZD) therapy in the past 12 months	Markers of interest will be altered by previous TZD exposure
Hypersensitivity of TZD	Contraindication to pioglitazone
New York heart association class III/IV heart failure.	Contraindication to pioglitazone
Known HIV positive	HIV/AIDS related cachexia may alter metabolic findings.
Pregnant or lactating women	Contraindication to pioglitazone. Pregnancy class C, not recommended in lactating women
History of, or active bladder cancer	Contraindication to pioglitazone
Inadequate hepatic function documented within 14 days of enrollment Total bilirubin level > 1.5 x ULN AST and ALT > 2.5 x ULN, unless there are liver metastases in which case AST and ALT or > 5 x ULN	TZD Clearance is significantly lower in hepatic impairment

X. Informed Consent Process

The research coordinator or the investigators will review the consent form with the subject page by page describing the purpose of the study, the research procedures, risks and alternatives. The subject will be given the opportunity to ask questions or voice concerns at this time. The informed consent counseling will take place in an area that provides privacy. The PI or co-investigator will describe all available options to potential patients, to answer questions, and to help the patients make participation decisions in a non-directive manner. The original signed informed consent document will be stored in a locked cabinet with the patient's case report forms (CRFs) in the Clinical Research Office (CRO), one copy will be given to the patient and one copy will be placed on the chart per institutional policy. Patients who are sedated or deemed emotionally or mentally unable to provide informed consent for any reason are not eligible for enrollment.

XI. Study Subject Identification Number

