All subjects will be assigned a study number that is not linked to their personal identifiers to prevent loss of confidentiality. The number will be the IRB Protocol Number followed by a sequentially number starting with number 01. For example, the first subject enrolled will be assigned study subject number 072012-036-01; the next will be 072012-036-02, and so forth. This number will be assigned by the Clinical Research Manager (CRM) upon confirmation of subject eligibility during the subject registration process. Subject registration will be confirmed once the following documents have been received by the CRM:

- Signed copy of the Informed Consent signature page
- Inclusion/Exclusion worksheet signed by the coordinator and treating physician

XII. Subject Registration

All study subjects must be entered into the Velos database in a timely manner after obtaining the informed consent of the subject. Following completion of baseline assessments and confirmation of subject eligibility, patients will be registered and assigned a subject identification number by the CRM, Subject registration will be confirmed (within 24 hours) once the following documents have been received by the CRM:

- Signed copy of the Informed Consent signature page
 - Inclusion/Exclusion worksheet signed by the coordinator and treating physician
- Since this is a double arm, pilot study, randomization to different treatment arms is not required.

XIII. Study Procedures and Treatment Plan

A. Screening Evaluations (for both treatment and control arms)

The following Screening assessments must be performed within 28 days before the first treatment of study drug:

1. Signed Informed Consent
2. Complete medical history (Med Hx), including documentation of current medications (CM), and Adverse Event (AE) assessment;
3. ECOG Performance Status
4. Complete Physical Examination (PE);
5. Vital Signs - BP, HR, RR, and Temp (°C)
6. Height (cm) and Weight (kg) (Record on weight log – see Appendix 2);
7. Laboratory requirements:
 - Hematology: CBC with differential and platelets
 - Serum Chemistry: Na, K, CL, Ca, CO₂, glucose, BUN, creatinine, AST, ALT, alkaline phosphatase, total bilirubin, total protein, albumin
 - Serum pregnancy test (women <60 years only)
8. Pathology report confirming adenocarcinoma histology
9. Staging work-up:
 - a. Posterior to anterior (PA) and lateral (LAT) chest x ray (unless CT chest done)

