Cost Coverage: UT Southwestern Medical Center - Touchstone Diabetes Center is covering the costs of the pioglitazone for subjects enrolled onto this study. Invoices for reimbursement must be interoffice mailed to [name] at mail code 8549. (Mailing Address: UT Southwestern Medical Center at Dallas, Touchstone Diabetes Center, [name], [name], [name] Attn: [name])

Dispensation: Each subject should be given a one month (28-day) supply of pioglitazone per cycle.

Accountability: The investigator and investigator site are responsible for maintaining an accurate inventory and accountability logs for the study drug, pioglitazone, for patients enrolled on this study. The site is permitted to use their own drug accountability form to record study drug dispensation and patient returned tablets. These forms should be stored in the site's dispensing pharmacy. Use of standard pharmacy accountability logs is acceptable.

2. Administration schedule:

Patients will be instructed to take pioglitazone (45mg daily by mouth) and will be instructed on how to take the pioglitazone for the entire cycle (one cycle equals 28 days). Subjects will continue taking pioglitazone daily for two cycles (no more than 8 weeks) or until one of the following criteria mentioned in section XIII D. Subjects will record their daily drug administration on a dosing diary, supplied by the study coordinator, in order to verify subject dosing compliance.

See table below for treatment schedule (cycle one and subsequent cycles)

Study Drug	Cycle 1				Cycle 2			
	Week 1	Week 2	Week 3	Week 4	Week 5	Week 6	Week 7	Week 8
Pioglitazone	daily	daily	daily	daily	daily	daily	daily	daily

D. Dose Modifications and Discontinuation

- Patients developing a treatment-related CTCAE v4 Grade 1 or 2 adverse event will have their dose continued at the same level.
- Pioglitazone must be held for any grade 3 or 4 toxicity until the event resolves to at least grade 2. Following the resolution, the dose of pioglitazone must be reduced to level -1.
- The following table describes potential dose level modifications for pioglitazone. If a subject requires a dose reduction is beyond level -2, pioglitazone must be discontinued.
- Patients removed from treatment for intolerable toxicity must be followed for evaluation of their time to disease progression (TDP).

Agent	Initial Dose	Level -1	Level -2
Pioglitazone	45 mg /day	30 mg/day	15 mg/day

For all toxicities:

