Standard symptomatic treatment will be offered by the treating physician. There is no dose modification of pioglitazone for grade 1 or grade 2 toxicity

Interruption in pioglitazone for greater than 14 days is not allowed. Subjects must discontinue treatment if this occurs.

- Hematologic Toxicities
There is no need to modify or discontinue pioglitazone due to hematologic toxicity.
- Diarrhea
For grade 3 or 4 diarrhea, hold pioglitazone until diarrhea resolves to ≤ grade 2, then it may be resumed at one lower dose level.
- Nausea and Vomiting
For grade 3 or 4 nausea or vomiting, hold pioglitazone until nausea and vomiting resolve to ≤ grade 2,

then it may be resumed at one lower dose level.

- Liver Function Tests

For grade 3 or 4 elevation of the liver function tests, hold pioglitazone until elevation of the liver function tests resolve to \leq grade 2, then gemcitabine and pioglitazone may be resumed at one lower dose level.

- Weight Gain

For grade 3 or 4 weight gain, hold pioglitazone until peripheral edema resolves to grade 2, then it may be resumed at one lower dose level.

E: Concomitant medication/Treatments:

Pioglitazone is metabolized through the cytochrome P450 2C8/9 and 3A4 pathways. The metabolic pathway of concomitant medications will be checked prior to prescribing with pioglitazone. According to the pioglitazone prescribing information, co administration of pioglitazone and gemfibrozil, a strong CYP2C8 inhibitor, increases pioglitazone exposure approximately 3-fold. Therefore, the maximum recommended dose of pioglitazone is 15 mg daily when used in combination with gemfibrozil or other strong CYP2C8 inhibitors.

Other strong CYP2C8 inhibitors include fluconazole, ketoconazole, nocardipine, sulfonamides, and some NSAIDs. Concomitant medications that are inhibitors of CYP 3A4 are likely to increase pioglitazone exposure as well and CYP 3A4 inducers may decrease pioglitazone concentrations.

Concomitant administration of pioglitazone with thioridazine is contraindicated

F. **Treatment Evaluations**

Same procedure will be followed for pioglitazone (treatment) and control arms except the control arm will not receive study drug (pioglitazone) and therefore will not have a pill diary

2-week visit (+/- 7 days)

- Symptom Driven Physical Examination (PE)
- Vital Signs - BP, HR, RR, and Temp ($^{\circ}$ C)
- Weight (kg, record on weight log)
- ECOG performance status
- AE/Toxicity assessment
- Laboratory assessments:

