9. 8. If performed within four (4) weeks of discontinuing pioglitazone, then not required to be completed (at the discretion of the investigator).. MRI will be done at Roger's MRI. Baseline MRI to be done before start of pioglitazone or within the first 7 days of starting pioglitazone (UT Southwestern and PHHS patients ONLY)
10. Follow up MRI can be done within 14 days of end of treatment. If patient does not complete 8 weeks but has completed 6-8 weeks of therapy, a follow up MRI should be done as if completed 8 weeks. MRI will be done on 8-10 patients chosen at PI/investigator discretion. (UT Southwestern and PHHS patients ONLY).

XIV. **Treatment Duration (N/A for control arm)**

Treatment will be continued for no more than **8 weeks** of therapy or unless the following events take place:

1. Patient withdraws consent.
2. Intercurrent illness that prevents further administration of pioglitazone
3. Unmanageable adverse events related to pioglitazone
4. General or specific changes in the patient's condition that in the judgment of the physician renders the patient unacceptable for further treatment with pioglitazone
5. Patient is lost to follow-up. Patient refuses to complete study procedures and scheduled appointments.
6. Patient requires more than two dose reductions
7. Interruption in study drug administration for greater than 14 days
8. Closure of the trial as deemed necessary by the principal investigator (PI), the UT Southwestern Institutional Review Board (IRB), the Simmons Comprehensive Cancer Center Data and Safety Monitoring Committee (DSMC) or the U. S. Food and Drug Administration (FDA).

XV. **Withdrawal of Subjects**

Patients can withdraw voluntarily if they are unable to continue with the treatment or for any other reasons. Patients will be encouraged to discuss withdrawal with their physician and the study team.

Patient who withdraw voluntarily will not be followed.

XVI. **Efficacy Assessments**

The following outcome measures are required to evaluate the safety and efficacy of pioglitazone:

1. Measurement of insulin resistance biomarkers: serum adiponectin level, oral glucose tolerance test, and fasting serum levels of glucose and insulin every four weeks.

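### With liver metastases and ALT above 2.5 and up to 5 x ULN, Section IX admits a patient whom the Safety Profile bars from pioglitazone, and no operative section says which limit governs dosing

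*Combined protocol and SAP*

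**What the plan says.** The hepatic row of the Section IX exclusion table, which uses values from within 14 days of enrolment, gives a bilirubin limit of 1.5 x ULN and then the transaminase limits: "AST and ALT > 2.5 x ULN, unless there are liver metastases in which case AST and ALT or > 5 x ULN". Its stated reason is that thiazolidinediones are cleared more slowly when the liver is impaired.

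The gastrointestinal and liver paragraph of the Safety Profile, in the background on pioglitazone, says "Liver enzymes, including serum ALT, need to be evaluated in all patients at initiation of therapy with pioglitazone, and periodically thereafter". It then says "If ALT >2.5X ULN at baseline or if the patient exhibits clinical evidence of active liver disease, pioglitazone will be discontinued". It does not mention liver metastases.

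Other relevant text:

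- Section VIII: "We plan to enroll fifteen patients with metastatic or locally advanced pancreas cancer". Liver metastases are therefore possible in this population.
- Sections IV and VIII: control patients meet the same criteria but receive no pioglitazone. The principal investigator or treating physician chooses the arm.
- Sections XI and XII: registration needs the signed consent page and an "Inclusion/Exclusion worksheet signed by the coordinator and treating physician".
- Section XIII.B: AST and ALT are measured on cycle 1 day 1, before the first dose. No action is attached to the result.
- Section XIII.D: "Pioglitazone must be held for any grade 3 or 4 toxicity until the event resolves to at least grade 2", and for the liver "For grade 3 or 4 elevation of the liver function tests, hold pioglitazone".
- Section XIV: the stopping list has no ALT limit. The nearest item is a change in condition that "in the judgment of the physician renders the patient unacceptable for further treatment with pioglitazone".

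**The concern.** The two ALT limits differ by a factor of two for patients with liver metastases, and both bear on whether a patient takes 45 mg daily, which the protocol describes as the maximum approved dose. Section IX's own reason for the row is drug clearance, so the limit is there to protect patients who are dosed.

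Registration runs on a worksheet built on the eligibility criteria. Staff who use Section IX alone could assign such a patient to pioglitazone and start treatment, although the Safety Profile says that the drug should not continue. A colleague who has read the Safety Profile might withhold the drug or use the control arm. Nothing in the protocol tells them to agree.

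The wording of the row is a secondary problem. It joins AST and ALT with 'and', which could mean that both must be raised, and the 5 x ULN clause contains a stray 'or'.

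**Working it through.** The plan gives no figure on this point, so the check is a comparison of rules.

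**Step 1. The rules as inputs.**

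- Section IX: the limit L is 2.5 x ULN, or 5 x ULN with liver metastases. The stray 'or' is ignored.
- Safety Profile: stop if baseline ALT > 2.5 x ULN, with or without metastases.
- Conflict: eligible under Section IX and stopped under the Safety Profile.

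Two readings of 'and' are tried. On the first, either enzyme above L excludes. On the second, both must be above L. Bilirubin is taken as acceptable, and the same enzyme values are assumed at screening and baseline.

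**Step 2. Example values, in multiples of ULN.**

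| Liver metastases | AST | ALT | Section IX, either excludes | Section IX, both needed | Safety Profile |
|---|---|---|---|---|---|
| yes | 3 | 2 | eligible | eligible | no bar |
| yes | 2 | 3 | eligible | eligible | stop |
| yes | 3 | 3 | eligible | eligible | stop |
| yes | 4.9 | 4.9 | eligible | eligible | stop |
| yes | 2 | 6 | excluded | eligible | stop |
| no | 2 | 3 | excluded | eligible | stop |
| no | 3 | 3 | excluded | excluded | stop |

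Rows two to four conflict on both readings. The core conflict (metastases, ALT above 2.5 and up to 5, AST not above 5) therefore does not depend on how 'and' is read. Rows five and six conflict only if both enzymes must be raised. On the either-enzyme reading, patients without metastases show no conflict.

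**Step 3. Is there a rule that settles it?** Section XIII.B obtains the baseline value but attaches no action to it. Section XIII.D responds to grade 3 or 4 toxicity and sets no baseline limit. Section XIV leaves the matter to physician judgment. None of them ranks one limit above the other.

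**Step 4. How many patients?** The background says that eighty percent of patients with pancreatic cancer present with distant metastases. It gives no figure for liver metastases, nor for ALT between 2.5 and 5 x ULN among them. No count among the 15 treated patients can be derived.

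**Step 5. Is the sample-size statement affected?** Section XX.A uses n = 15, mean change 0.4, SD 0.5 and a 0.05 level. A two-sided one-sample t-test has noncentrality (0.4/0.5) x √15 = 3.098 on 14 degrees of freedom, which gives power 82.1% against the stated 82%. The hepatic limits are not an input, so this figure does not change.

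**The case against.** The strongest reply is that the two texts are compatible. Section IX governs entry to both arms, and control patients take no drug. Arm assignment is discretionary, and the list of possible control patients ends with a catch-all left to the investigators. A patient with metastases and ALT of 3 x ULN can thus be validly enrolled and kept off pioglitazone. The timing also fits: Section IX looks at the 14 days around enrolment, while the Safety Profile looks at baseline and so could serve as a separate pre-dose check. This stands, and it means that a reader who infers that the protocol cannot be followed goes too far. It does not supply the missing instruction, because no section tells staff to take that course.

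A second reply is that the Safety Profile is loose background. It speaks of discontinuing a drug not yet started. It also says that patients with pre-existing cardiac disease will be excluded, whereas Section IX excludes only NYHA class III/IV heart failure. A deliberate metastases clause in the eligibility table might naturally prevail. That is a fair guess about intent, but the sentence is worded as an instruction and nothing says that Section IX overrides it.

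Third, practical safeguards exist. The treating physician signs the worksheet, chemistry is repeated at weeks 2, 4, 6 and 8, grade 3 or 4 liver elevations require a hold, and treatment lasts at most 8 weeks. These limit harm on treatment but leave the baseline decision open.

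Finally, a reader might infer from the literal 'and' that the trial means to admit isolated ALT elevations of any height. The row's heading (inadequate hepatic function) and its reason suggest that each enzyme was meant, so this is a drafting ambiguity. The layout of the cell may also have been altered when the text was extracted.

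**Conclusion.** The inconsistency is real and narrow. It concerns patients with liver metastases and ALT above 2.5 and up to 5 x ULN, with AST and bilirubin within limits, who are candidates for the pioglitazone arm. For them the protocol gives two ALT limits and does not say which one governs dosing. This rests on reading the Safety Profile sentence as an instruction and on the enzyme value being similar at screening and at baseline.

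Its size in patients is unknown. Counting combinations of enzyme bands would not measure it, because the count depends on how the bands are drawn. A reader might also infer that the trial's power or primary analysis is compromised, but the documents do not support that: no stated figure depends on this limit. The point deserves correction because it concerns a drug-safety limit and is cheap to settle.

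**What to change.** 1. Reword the transaminase part of the Section IX row as: *AST or ALT > 2.5 x ULN (AST or ALT > 5 x ULN if liver metastases are present)*.
2. State one pre-dose ALT limit for the pioglitazone arm in Section XIII, and make the Safety Profile match it. There are two options:
   - **5 x ULN when liver metastases are present.** Add this exception to the Safety Profile sentence, and say that liver metastases alone do not count as active liver disease. Otherwise the second half of that sentence could still bar the same patients.
   - **2.5 x ULN for all pioglitazone patients.** Patients with liver metastases whose ALT is above 2.5 and up to 5 x ULN then remain eligible for the control arm only.

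The choice is clinical and belongs to the investigators. Simply deleting the metastases allowance from Section IX would be a poorer remedy, because it would also shut these patients out of the control arm, where the drug-clearance reason does not apply.

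The cost is one table row, one line in Section XIII and one sentence in the Safety Profile. Patients with a single raised enzyme, whom the literal wording would admit, are excluded. The first option relaxes the limit now written in the Safety Profile. The second could slow accrual to the pioglitazone arm and would make the arms differ in baseline ALT, which should be noted when the non-randomised, exploratory comparison is reported.

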 - b. CT scan of abdomen and pelvis with IV and PO contrastFollowing completion of the pretreatment assessments and confirmation of eligibility, patients will be registered, assign a subject identification number, evaluated and followed up according to the study procedures described below. Since this is a double arm, pilot study,

randomization to different treatment arms is not required.

B. Week 0 (**Baseline evaluation**)

The following baseline evaluations assessment will be performed on cycle 1 day 1 prior to the first dose of study drug: Control arm patients will have the same evaluation but will not receive study drug)

- Complete Physical Examination (PE)
- Vital Signs - BP, HR, RR, and Temp (°C)
- Weight (kg, record on weight log)
- ECOG Performance Status
- AE/Toxicity Assessment
- Laboratory assessments:
 - Hematology: CBC with differential and platelet count
 - Serum chemistry: Na, K, Cl, Ca, bicarbonate, BUN, creatinine, AST, ALT, alkaline phosphatase, total bilirubin, total protein, albumin
 - Pregnancy test (WOCBP ONLY)
 - CA19-9
 - C-reactive protein level
 - Serum fasting glucose (fasting for at least 8 hours)
- Exploratory Research Lab Evaluations
 - Glucose tolerance test (0 baseline and 2 hr ingestion)
 - Insulin level (0 hr baseline and 2 hr post ingestion)
 - Adiponectin (0 hr baseline)

 - MCP-1 level (0 hr baseline)
- FACT-Hep Questionnaire

- MRI abdomen noncontrast (Research) Should be done +/- 7 days of starting pioglitazone (7 days pre or 7 days after starting pioglitazone) MRI will be done on 8-10 patients chosen at PI/investigator discretion (UT Southwestern and PHS patients ONLY).

C. **Treatment Plan**

1. **Prescription Information**

How Supplied: Pioglitazone is available in 15 mg, 30 mg, and 45 mg tablets. The 15 mg tablets are white to off-white, round, convex, non-scored tablets with "ACTOS" on one side and "15" on the other side. The 30 mg and 45 mg tablets are white to off white, round, flat, non-scored tablets with "ACTOS" on one side and "30" or "45" (respectively) on the other side. Availability: Each (15 mg, 30 mg and 45 mg) are available in bottles of 30, 90 or 500.

Storage: Pioglitazone should be stored at 25 °C (77°F); excursions permitted to 15-30°C (59-86°F). Keep the container closed tightly, and protect from moisture and humidity.

Ordering: The investigational drug pharmacist will purchase a bulk (cost efficient) supply of pioglitazone and dispense to study participants.

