 - Hematology: CBC with differential and platelet count
 - Serum chemistry: Na, K, Cl, Ca, bicarbonate, BUN, creatinine, AST, ALT, alkaline phosphatase, total bilirubin, total protein, albumin
 - C-reactive protein level
 - Serum fasting glucose (fasting for at least 8 hours)
- Exploratory Research Lab Evaluations
 - Insulin level (0 hr baseline)
 - Adiponectin (0 hr baseline)

 - MCP-1 level (0 hr baseline)

4 Week Visit (+/- 7 days)

- Symptom Driven Physical Examination (PE)
- Vital Signs - BP, HR, RR, and Temp ($^{\circ}$ C)
- Weight (kg, record on weight log)
- ECOG Performance Status
- AE/Toxicity assessment

- Laboratory assessments:
 - Hematology: CBC with differential and platelet count
 - Serum chemistry: Na, K, Cl, Ca, bicarbonate, BUN, creatinine, AST, ALT, alkaline phosphatase, total bilirubin, total protein, albumin
 - CA19-9
 - C-reactive protein level
 - Serum fasting glucose (fasting for at least 8 hours)
- Exploratory Research Lab Evaluations
 - Glucose tolerance test (0 baseline and 2 hr post ingestion)
 - Insulin level (0 hr baseline and 2 hr post ingestion)
 - Adiponectin (0 hr baseline)
 - MCP-1 level (0 hr baseline)
- FACT-Hep Questionnaire
- Review of Patient Pill Diary
- Patient will receive 4 week refill of Pioglitazone

6-week visit (+/- 7 days)

- Symptom Driven Physical Examination (PE)
- Vital Signs - BP, HR, RR, and Temp (°C)
- Weight (kg, record on weight log)
- ECOG Performance Status
- AE/Toxicity assessment
- Laboratory assessments:
 - Hematology: CBC with differential and platelet count
 - Serum chemistry: Na, K, Cl, Ca, bicarbonate, BUN, creatinine, AST, ALT, alkaline phosphatase, total bilirubin, total protein, Albumin
 - C-reactive protein level
 - Serum fasting glucose (fasting for at least 8 hours)
- Exploratory Research Lab Evaluations
 - Insulin level (0 hr baseline)
 - Adiponectin (0 hr baseline)
 - MCP-1 level (0 hr baseline)

8 week visit (+/- 7 days)

- Symptom Physical Examination (PE)
- Vital Signs - BP, HR, RR, and Temp (°C)
- Weight measurement (kg, record on weight log)
- ECOG performance status
- AE/Toxicity Assessment
- Laboratory assessments:
 - Hematology: CBC with differential and platelet count
 - Serum chemistry: Na, K, Cl, Ca, bicarbonate, BUN, creatinine, AST, ALT, alkaline phosphatase, total bilirubin, total protein, albumin
 - CA19-9
 - C-reactive protein level
 - Serum fasting glucose (fasting for at least 8 hours)
- Exploratory Research Lab Evaluations

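### A 28-day first supply and a week-4 refill visit that may be 7 days late can leave a fully adherent patient without drug for up to 6–7 days before the week-4 draw

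*Combined protocol and SAP*

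**What the plan says.** Section XIII.C sets the supply: "Each subject should be given a one month (28-day) supply of pioglitazone per cycle". A cycle is 28 days, and the treatment table shows daily dosing in each of weeks 1 to 8 with no break between cycles. The Appendix 3 diary tells patients to take one tablet a day, so a cycle's supply is 28 tablets. The same section describes the stock: the tablets "are available in bottles of 30, 90 or 500". On ordering it says: "The investigational drug pharmacist will purchase a bulk (cost efficient) supply of pioglitazone and dispense to study participants".

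The visit lists in XIII.F name one refill. It falls at the visit headed "4 Week Visit (+/- 7 days", where the list includes "Patient will receive 4 week refill of Pioglitazone" and "Review of Patient Pill Diary". The week-2 list contains no dispensing. No overage, early pick-up or bridging supply is described anywhere. Section XIII.D requires discontinuation only when an interruption exceeds 14 days.

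The week-4 visit takes fasting glucose, the oral glucose tolerance test (OGTT), insulin at 0 and 2 hours, and adiponectin. Under section VII, primary end points (a) adiponectin and (b) OGTT use baseline and week 8. End point (c) uses fasting glucose and insulin every four weeks.

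**The concern.** Three rules that are each reasonable do not fit together. The supply equals the cycle length, the refill is tied to a visit, and that visit may be a week late without a deviation. A patient who does everything asked can therefore run out.

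The week-4 blood is drawn at the visit that supplies the refill, so any drug-free days come directly before sampling. Such a value could then be read as an on-treatment value, and nothing in XX.B separates it from the others. Week 4 matters in these places:

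- It is one of two on-treatment readings on the four-weekly schedule of end point (c). On the fuller XIII.F visit lists it is one of four (weeks 2, 4, 6 and 8). The Schedule of Events shows insulin but no fasting glucose at weeks 2 and 6.
- It is one of two on-treatment OGTTs.
- It is one point in the XX.B plots of biomarker change over time.

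**Working it through.** **The plan's own figure.** Section XX.A gives 82% power for n = 15, mean relative change in adiponectin 0.4, SD 0.5 and significance level 0.05. A two-sided one-sample t-test has effect size 0.4/0.5 = 0.8 and noncentrality 0.8 × √15 = 3.10 on 14 degrees of freedom. Its power is 82.1%, so the figure is reproduced. No week-4 value enters it.

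**Length of the gap.** The first dose is on day 1 (section XIII.B). N tablets then cover days 1 to N, and dosing resumes on visit day V, so

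gap = max(0, V − (N + 1)).

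The protocol does not say whether week 4 is day 28 or day 29, so both are shown. Each window has 15 days.

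| Tablets given | Week 4 = day 28 (V = 21–35) | Week 4 = day 29 (V = 22–36) |
|---|---|---|
| 28 | gap if V = 30–35: 6 of 15 days, at most 35 − 29 = 6 | gap if V = 30–36: 7 of 15 days, at most 36 − 29 = 7 |
| 30 | gap if V = 32–35: 4 of 15 days, at most 35 − 31 = 4 | gap if V = 32–36: 5 of 15 days, at most 36 − 31 = 5 |
| 35 | none | none (36 − 36 = 0) |

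These are counts of calendar days in the window and do not say how often late visits occur. Appendix 3 tells patients not to make up a dose missed until the next day. Each such dose leaves a tablet over and shortens the gap by one day.

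**Doses by day 56.** With 28 tablets first and a refill on day 35, doses taken are 28 + (56 − 35 + 1) = 50. With a refill on day 36 they are 28 + (56 − 36 + 1) = 49. The plan is 56. This counts the 8-week limit by calendar from day 1.

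**Drug level at the draw.** The pharmacokinetics paragraph gives a half-life of 16–24 hours for total pioglitazone. Assuming simple exponential decline, the level relative to the usual pre-dose level is 0.5^(24 × gap / half-life):

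- gap 6: 0.20% (16 h) to 1.56% (24 h)
- gap 7: 0.07% to 0.78%
- gap 4: 1.56% to 6.25%
- gap 5: 0.55% to 3.13%

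The longest gap therefore leaves 0.07–1.6% with 28 tablets and 0.55–6.3% with 30. These are serum levels only.

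**Later draws.** The same paragraph says steady state is reached within 7 days. The week-6 window opens on day 42 − 7 = 35 or 43 − 7 = 36, the same day as the latest refill. An early week-6 draw can thus follow fewer than 7 days of resumed dosing. An on-time week-8 draw follows 56 − 35 = 21 (or 57 − 36 = 21) days of resumed dosing. One taken 7 days early follows 49 − 35 = 14 (or 50 − 36 = 14).

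**Patients affected.** The documents give no visit-timing data. If 5%, 10% or 20% of week-4 visits fell after the supply ended (an assumption), that would be 15 × 0.05 = 0.75, 15 × 0.10 = 1.5 or 15 × 0.20 = 3 patients.

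**The case against.** The strongest reply is that the gap rests on silence. The supply is due per cycle, so the second one could be read as due on day 29. A pharmacist holding bulk stock dispenses the drug, and nothing makes the week-4 visit the only permitted refill route. A sensible pharmacy might simply hand over tablets when they are due. That stands in part, and it is why the point is conditional. But the visit lists name the refill at one visit only, and they let that visit be late, so a site following them as written can produce the gap. The 14-day rule in XIII.D stops treatment after a long interruption and does not prevent a shorter one.

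It is also fair that the full gap needs perfect adherence, a visit on the last window day and no pharmacy contact in between. Nor is the gap hidden: the diary has a date column and is reviewed at that visit, and dispensing logs are kept. With only 28 rows in the diary, however, the gap has to be worked out from the dates.

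A reader might infer that the gap undermines the primary result. The documents do not support that. End points (a) and (b) use week 8, at least 14 days of resumed dosing precede an early or on-time week-8 draw, and no test in section XX is tied to a week-4 value. A reader might also take the very low drug levels to mean that the biomarkers have returned to baseline. That does not follow either, since the drug is described as acting through transcription and the documents give no time course for loss of effect.

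The 8-week visit has the same window, so a late week-8 draw can also follow drug-free days. That arises from the dosing cap and not from the supply. It is a separate question, which the change below does not address.

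**Conclusion.** The conflict between the supply and visit rules is real and modest. As written, an adherent patient seen late but in window can have up to 6–7 drug-free days before the week-4 draw, or 4–5 with a 30-tablet bottle. The values at risk are the week-4 readings of end point (c), the week-4 OGTT and adiponectin in descriptive displays, and possibly an early week-6 draw. Doses taken by day 56 can fall to 49–50 of 56. The powered adiponectin test and its 82% power are not affected.

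This rests on one tablet a day from day 1, week 4 meaning day 28 or 29, and no off-visit refill. The calendar arithmetic is firm. The number of patients affected is unknown, and the effect on any biomarker cannot be derived. The point is a cheap improvement to consider, not a threat to the trial's main conclusion.

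**What to change.** In XIII.C, dispense 35 tablets at baseline and 21 at the week-4 visit, and change the refill line in XIII.F to match. The first supply then covers every day of the week-4 window under either day count. The total stays at 35 + 21 = 56, so the supply still equals the 8-week cap. Giving 35 and then 28 would put 63 tablets in patients' hands, 7 beyond the cap.

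Extend the cycle 1 diary in Appendix 3 to 35 dated rows. In the XX.B plots, identify any week-4 value drawn after one or more drug-free days, using the diary dates and the dispensing log.

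The cost is slightly more drug accountability work, up to 7 more tablets at home during cycle 1, 7 more diary rows and a plot marker. No extra drug is needed overall, and because the pharmacist dispenses from bulk stock, no special pack size is needed.
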